Intense therapeutic ultrasound (ITU). Various types of ultrasound have been used to treat soft tissue injuries since the 1930s. Intense therapeutic ultrasound (ITU) is a recently developed ultrasound based therapy in which sound waves are concentrated to produce selective thermal coagulative change over a small area while leaving the remaining regions unaffected. ITU has been used clinically for treating the facial skin for the past decade and it has recently received FDA approvals for non-surgical brow and submental tissue lifting. Over 300,000 patients worldwide have been treated using this technology. Clinical studies have shown that 85% of subjects receiving this treatment on facial skin tissue showed an improvement in facial lifting with no significant pain, erythema, inflammation or scarring. Histologically, it has been shown that ITU induces the production of dermal collagen with thickening of the dermis and straightening of the elastic fibers in the reticular dermis. On-going research in our laboratory has shown that ITU can improve healing of damaged Achilles tendon in a rabbit model. Preliminary results showed an increase in markers for wound healing (e.g. VEGFa, TNF α , IL-1 β , and TGF β 1) and a decrease in markers for scar tissue formation (e.g. COL1 α 1, COL1 α 2, and COL2 α 2) in injured rabbit tendon treated with ITU compared to injured, untreated rabbit tendon. These results have led us to want to explore the possibility using ITU to treat patients with CPF.

2) Lay Summary (approximately 400 words)

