Interested individuals who contact the laboratory will have the logistics of the study explained and be referred to the clinic for diagnosis and treatment of heel pain. All patients diagnosed with plantar fasciitis by participating physicians will be contacted by the research team to discuss the details associated with participation. We would like to obtain a temporary deferment of authorization to obtain contact information from the electronic medical record for those individuals who are initially identified in the clinics by participating physicians. Additionally, we would like permission to provide the consent and authorization forms and other information by e/mail should this be conducive to obtaining informed consent. The mailing is for informational purposes only to allow the subject more time to consider participation in the study. The informed consent process will be completed in person. Both English and Spanish versions of the consent forms will be utilized, although the Spanish consent form will be submitted as a modification once the English version is approved. Finally, we would like to provide a map and information sheet to assist participation in the study (see attachments).

7) Procedures involved in the Human Research

After obtaining informed consent and authorization from the subject, study personnel will verify the screening of participants utilizing the inclusion/exclusion criteria and collect the following information- age, gender, height, weight, activity level, pain level, and physical exam findings including x-rays - which will be recorded on the data abstraction sheet (see attachment). The activities strictly associated with the research are the assignment to a study group (Control or ITU), the administration of patient reported outcome measures (questionnaires), and therapeutic and/or diagnostic ultrasound (Table 1). Additionally, adverse events will be recorded at each visit (see attachment). Treatment tolerability will be prior to, immediately after, and at 2 days post-treatment.

Standard of care is integrated into both arms of the investigation and includes a structured physical examination, the use of an NSAIDs for 3 weeks (Naprosyn 500 mg po bid or Ibuprofen 800 mg po tid taken with meals), viscoelastic heel cups for 12 weeks, and supervised physical therapy with home exercise program for 6 weeks. These components are described below-

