Assessment of Safety and Tolerability (Aim 3). Subject self-assessments of treatment tolerability will be conducted immediately after, two days after (phone survey) and two weeks after treatment using a 10-point visual analog scale (VAS, see Appendix 1-C). The subject will be asked to report their current level of pain and the maximum level of pain experienced over the last two days. The VAS is the standard for assessing pain for both clinical and research purposes. Recording of adverse events will take place at all visits (see adverse event reporting form Appendix 4 in the protocol). Adverse events and serious adverse events will be monitored throughout the study. A treatment will not be administered if there is residual pain/discomfort experienced by the subject from the previous treatment.

Statistical analysis. Data will be assessed for variance homogeneity and normality. FFI-P, PFCAT, and FAAM scores before and after intervention will be compared between the two groups using a paired t-test. Additionally, the mean thickness of the plantar fascia will be compared between the two groups before and after treatment and significance determined utilizing paired t tests. P<0.05 is considered to be statistically significant.

8) Risks to subjects

Exposure to ITU may produce short-term sensations which may cause discomfort and mild erythema for up to a few hours following the exposure. No detrimental side effects have been reported in previous clinical trials investigating similar devices in which ultrasound energy was applied to the neck and face. Additionally, the ITU in this investigation will utilize lower power parameters than those reported for these similar devices. We are seeking classification of the GEN II system (Guided

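### No described assessment asks about erythema, other skin change or altered sensation, so the stated hours-long duration of erythema is not systematically checked

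*Protocol*

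**What the plan says.** Safety and tolerability of ITU are Aim 3 of the protocol. Four places in Section 3 bear on how they are assessed.

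- **Named risk**: "Exposure to ITU may produce short-term sensations which may cause discomfort and mild erythema for up to a few hours following the exposure" (item 8, Risks to subjects).
- **Tolerability** (item 7, Assessment of Safety and Tolerability): "Subject self-assessments of treatment tolerability will be conducted immediately after, two days after (phone survey) and two weeks after treatment", on a visual analog scale (VAS). The content described is "The subject will be asked to report their current level of pain and the maximum level of pain experienced over the last two days". The opening paragraph of item 7 gives a different set of times: "Treatment tolerability will be prior to, immediately after, and at 2 days post-treatment".
- **Adverse events** (same Aim 3 paragraph): "Recording of adverse events will take place at all visits", using the Appendix 4 form. The paragraph adds that adverse events are monitored for the whole study, without saying how this is done between visits.
- **Schedule** (Table 1 and the treatment paragraph): treatments at weeks 0 and 2, then visits at weeks 4, 6 and 12.

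The focused examination covers alignment, swelling, palpation, range of motion and a squeeze test. It lists no skin inspection and no sensory test. The SAP contains no analysis of adverse events or skin findings.

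**The concern.** The protocol names two effects of the device and gives both a duration of hours. It then describes an instrument for only one of them. Discomfort is scored on the VAS, while erythema has no described question, examination item or time point.

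This matters for a pilot with a safety aim. In ITU, "sound waves are concentrated to produce selective thermal coagulative change over a small area", and here the thermal zones are centred 10–13 mm deep along the plantar fascia. The human experience that the protocol cites is with the face and neck. How often the skin or sensation is affected at the new site, and for how long, is part of what Aim 3 should describe. Suppose a reaction causes little pain, appears after the subject leaves and clears before the next visit. It enters the data only if the subject volunteers it or remembers it up to two weeks later. Reports gathered that way tend to be incomplete, and a low count could not be read as evidence that the reactions were rare or brief.

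**Working it through.** No sample-size or error-rate figure is involved. The check sets the window of the named risk against the timing and described content of each contact.

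**Contacts after one treatment** (item 7 and Table 1)

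| Time from treatment | Contact | Described content | Skin or sensation asked? |
|---|---|---|---|
| 0 h | Treatment visit | VAS; adverse event recording | Not described |
| 48 h | Phone survey | Current pain; maximum pain over two days | Not described |
| 14 days | Next visit | VAS (in one of the two lists); adverse event recording; focused examination | Not described |

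**Length of the gap.** Week 0 to week 2 is 14 days, and week 2 to week 4 is 14 days. Each gap holds one scheduled research contact, the call.

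**Position of the risk window.** The window opens at the treatment visit, where adverse events are recorded. The documents do not put a number on a few hours. On any reading below 48 hours, the window closes before the next scheduled research contact, so its end is not observed directly.

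**What the pain items cover.** At the call, maximum pain over two days looks back 48 hours, to about the time of treatment. It captures the peak of any discomfort but not its duration. If the same question is asked at two weeks, it covers days 12 to 14.

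**Number of treatments affected.**
- Enrolment 50, allocation 1:1: 50 / 2 = 25 per arm.
- ITU treatments: 25 × 2 = 50.
- Calls in both arms, if sham sessions follow the same schedule: 50 × 2 = 100.

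**Other contacts in the gap.** Standard of care includes supervised physical therapy twice a week for 6 weeks, with no start date given. If it runs from week 0, that is 2 per week × 2 weeks = about 4 in-person contacts per gap. For the first gap the range is 0 to 4. The documents do not ask therapists to look for or report reactions.

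**The case against.** The strongest case on the other side has five parts.

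1. **The call may not be the only contact.** Physical therapy, which includes massage of the plantar fascia, probably brings subjects in between visits. This stands, so the point is confined to scheduled research contacts. Because therapists are given no reporting role, these contacts do not amount to described ascertainment.
2. **Adverse events are recorded at the treatment and week-2 visits and monitored throughout.** This also stands. A reader might infer that the erythema statement cannot be checked at all. The documents do not support that: redness can be recorded at the session, recalled at two weeks, or seen then if it persists. What is missing is a systematic check.
3. **The text does not limit the call to pain, and the appendices are not in the reviewed text.** A skin item in Appendix 1-C or on the Appendix 4 form cannot be excluded. The finding therefore concerns what is described. The Appendix 4 form is tied to visits rather than to the call.
4. **Some tempting inferences go beyond the text.** A reader might infer that the few-hours figure was taken from face and neck devices. The neighbouring sentence on those devices concerns the absence of detrimental effects, and the source of the figure is not stated. The protocol also says that lower power will be used here. A reader might further infer that numbness would lower the VAS, or that events will be missed mainly in the ITU arm. Both are possible, but the documents give no event rate and show neither.
5. **The named sign is mild and brief, and a day-2 answer is still recall.** Both are true. Recall over two days is nonetheless shorter than recall over fourteen, and the call is already planned.

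**Conclusion.** The concern holds in a limited form. As described, no assessment solicits erythema, other skin change or altered sensation, or records their duration. The one scheduled research contact in each 14-day gap is described as asking about pain, while adverse event recording is tied to visits. For a named risk lasting hours, Aim 3 would rest on unsolicited reports or two-week recall.

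The size is two gaps per subject and about 50 ITU treatments. That is a count of exposures under incomplete ascertainment and says nothing about how many reactions would be missed. The conclusion assumes that the unseen appendices add no skin or sensation item to the call and that full enrolment of 50 splits evenly.

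This is a worthwhile, inexpensive improvement to safety data collection and does not affect the efficacy comparison. Separately, the two lists of tolerability time points in item 7 disagree: one includes a pre-treatment assessment and omits two weeks, and the other does the reverse.

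**What to change.** In Section 3, item 7, Assessment of Safety and Tolerability:

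- Name the day-2 call as an adverse event collection point.
- Add three yes/no items to its script: redness or other skin change; numbness or tingling; any other problem. For each positive answer, record onset and end time.
- Use the same wording in both arms after both sessions. Log positive answers on the Appendix 4 form through staff who already know the assignment, so that reports do not hint at it to blinded staff. A fixed script limits uneven probing by those staff.
- Reconcile the tolerability time points here with those in the opening paragraph of item 7.

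The change concerns data collection only and sets no rule about giving or withholding treatment.

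**Cost.** A few script lines and a few more minutes per call, over at most about 100 calls. Solicited questions will bring in some non-specific reports, and the sham arm shows how many to expect. The answers remain short recall, so onset and end times within the first hours will be approximate.

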**FORM: Application for Human Research**

NUMBER	FORM DATE	PAGE
F200		10 of 18

Table 1. Calendar of Activities

Timeline	Standard of Care	Research Activity
-1	focused history, x-rays, NSAIDs, heel cups	Informed consent and assessment of inclusion/exclusion criteria; enrollment in the study (randomization to treatment group)
0	NSAIDs, heel cups, focused exam	questionnaires; ultrasound (diagnostic & treatment)
2 weeks	NSAIDs, heel cups, focused exam	questionnaires; ultrasound (diagnostic & treatment)
4 weeks	heel cups, focused exam	questionnaires ultrasound (diagnostic)
6 weeks	heel cups, focused exam	questionnaires ultrasound (diagnostic)
12 weeks	heel cups, focused exam	questionnaires ultrasound (diagnostic)
24 weeks		questionnaires

Structured physical examination. The focused exam will consist of assessment of hindfoot and midfoot alignment, inspection for swelling, palpation of the calcaneus and entire plantar fascia, range of motion of the ankle with the knee flexed and with the knee extended, and calcaneal squeeze test. Pertinent positive findings on exam include: valgus hindfoot, midfoot planus, tenderness to palpation at the insertion of the plantar fascia onto the calcaneus, ankle dorsiflexion less than 10 degrees with the knee extended or greater than 10 degree augmentation in ankle dorsiflexion with the knee flexed. Pertinent negative findings include: lack of swelling at the ankle and midfoot, no tenderness at the Achilles insertion, the retrocalcaneal bursae, along the arch, posterior to the medial malleolus, or at Baxters point, and positive calcaneal squeeze test.

Physical Therapy. Supervised physical therapy will occur two times per week and include gastrocnemius stretching, plantar fascia specific stretching, modalities (ice and heat), and plantar fascia deep tissue massage (see instructions to PT appendix 2 of the protocol). Use of advanced modalities such as iontophoresis, phonophoresis, or TENS will not be permitted. The home exercise program will consist of PF specific stretch and gastrocnemius stretch to be done for ten minutes two times per day (see home exercise program handout, Appendix 2 of the protocol). Subjects will be required to record the frequency of each exercise in a logbook (see Appendix 3 of the protocol).

The research components are described below-

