In addition to the 11-point VAS pain scale, patients self-reported answers to questions from the Foot Function Index (FFI) pain subscale questionnaire, which has been standardized in a number of PF-focused publications [8-10]. Scores range from 0-90, with 0 indicating no pain and 90 indicating the worst pain imaginable in a variety of daily activities involving use of the plantar fascia. Self-reported scores were taken at baseline and each follow-up timepoint. The average score for each timepoint were calculated, and follow-up averages were compared to baseline to calculated the percentage reduction in score.

- Statistical Calculations

Student T-tests were utilized to determine statistically significant differences between baseline and subsequent follow-up measurements for self-reported and lesion size measurements. The level of significance ( $\alpha$ ) was set to 0.05.

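### Each subject's baseline is used only by pairing, differencing or ratio, never as a covariate in an ITU-versus-sham comparison, so a 50-subject trial gives up precision it could have without new data

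*Protocol*

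**What the plan says.** **Objective.** Aims 1 and 2 (Protocol, Section 3, Background) are comparisons of ITU plus standard care with sham plus standard care. Target enrolment is 50, allocated 1:1.

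**Baseline data.** The calendar (Protocol, Table 1) lists "questionnaires; ultrasound (diagnostic & treatment)" at week 0, and the same entry at week 2. The Patient Reported Outcome Measures paragraph confirms that questionnaires are completed before treatment starts. The Diagnostic Ultrasound paragraph calculates change in thickness from baseline.

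**Protocol analysis.** For FFI-P, PFCAT and FAAM, "scores before and after intervention will be compared between the two groups", and the method named is a paired t-test. Mean thickness is "compared between the two groups before and after treatment and significance determined utilizing paired t tests".

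**SAP analysis.** Pain is turned into each subject's percentage change from their own baseline, which classifies the subject against a 25% goal. Each lesion's volume is divided by its own baseline volume. For the FFI only, "follow-up averages were compared to baseline to calculated the percentage reduction in score". The tests are these: "Student T-tests were utilized to determine statistically significant differences between baseline and subsequent follow-up measurements for self-reported and lesion size measurements". PFCAT, FAAM and fascia thickness do not appear in the SAP.

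Neither document names a covariate, ANCOVA, regression or repeated-measures model.

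**The concern.** Two weaknesses sit in the same sentences.

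- **No named test compares the arms.** A paired t-test compares two measurements on the same subjects. The SAP's tests compare follow-up with baseline. Neither tests ITU against sham.
- **The obvious repair is still inefficient.** A two-sample t-test on change from baseline would be valid. But subtracting the whole baseline over-corrects whenever the baseline-to-follow-up correlation is below 1 and the SDs are similar. Entering the baseline as a covariate lets the data set the size of the correction.

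With about 25 subjects per arm, only large differences can be detected. The baseline is already collected, so the extra precision needs no further subject or visit.

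**Working it through.** **Inputs from the documents.** 50 subjects at 1:1, so n = 25 per arm. Significance level 0.05 ("P<0.05 is considered to be statistically significant"); sidedness is not stated, so I take it as two-sided.

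**Inputs assumed.** The documents give no SD, target effect, power, dropout or baseline-to-follow-up correlation (ρ). I work in SD units with equal SDs at baseline and follow-up, 80% power, no dropout, and ρ = 0.3, 0.5 and 0.7. The figure of 50 has no stated derivation, so there is nothing to reproduce.

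**Variance factors**, in units of the follow-up variance:
- change score: 2(1 − ρ)
- ANCOVA: 1 − ρ²
- ratio of ANCOVA to change score: (1 − ρ²) / [2(1 − ρ)] = (1 + ρ)/2

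**Anchor.** For a two-sample t-test with 25 per arm and variance factor 1, the difference detectable with 80% power is 0.809 SD (noncentral t). For another factor, multiply 0.809 by its square root. For ρ = 0.5, change score: 0.809 × √1.00 = 0.81; ANCOVA: 0.809 × √0.75 = 0.70.

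| ρ (assumed) | Change-score factor | ANCOVA factor | Ratio | Detectable difference, change → ANCOVA (SD) | Power at a true 0.7 SD, change → ANCOVA |
|---|---|---|---|---|---|
| 0.3 | 1.40 | 0.91 | 0.65 | 0.96 → 0.77 | 54% → 72% |
| 0.5 | 1.00 | 0.75 | 0.75 | 0.81 → 0.70 | 68% → 80% |
| 0.7 | 0.60 | 0.51 | 0.85 | 0.63 → 0.58 | 88% → 92% |

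Put as sample size, 50 subjects analysed by ANCOVA are worth 50/0.65 ≈ 77, 50/0.75 ≈ 67 or 50/0.85 ≈ 59 analysed by change score.

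**Small-sample check.** Estimating the slope inflates the ANCOVA variance by about 1 + 1/46 and leaves 47 degrees of freedom. The detectable differences become 0.78, 0.71 and 0.58 SD, and the power at 0.7 SD becomes 71%, 79% and 92%.

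**Simulation check.** With 8,000 trials per ρ, 25 per arm and a true difference of 0.8 SD, power for change score and ANCOVA was 65% and 82% at ρ = 0.3, 80% and 89% at 0.5, and 95% and 97% at 0.7. ANCOVA was the more precise each time.

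**Why within-arm tests cannot stand in.** Suppose both arms improve by the same 0.5 SD and ρ = 0.5. The SD of change is √(2 × 0.5) = 1, so the noncentrality is 0.5 × √25 = 2.5 on 24 degrees of freedom, and each paired test has 67% power. The chance that exactly one arm reaches significance is 2 × 0.67 × 0.33 ≈ 44%, with no treatment difference at all.

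**The case against.** **Baseline is not ignored.** A reader might infer that the plan compares raw scores and disregards each subject's own starting value. The documents do not support that. A paired test subtracts the subject's baseline, the Protocol calculates change in thickness, and the SAP uses per-subject percentage change for pain and per-lesion ratios for volume. A reader might also take percentage reduction of group averages to be the SAP's method for every outcome; it is stated for the FFI only. What remains is that baseline is never a covariate.

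**The size is uncertain.** No correlation is given. At 0.7 the gain over a change score is small. This stands, and it is why the range is shown. But ρ is not known in advance, and in large samples ANCOVA is at least as precise as a change score at any value.

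**Chance imbalance is not a bias.** One might argue that simple randomisation leaves the arms unequal at baseline and so biases the result. Imbalance arising by chance is already reflected in the unadjusted standard error. Even/odd allocation is also offered only as an example of an algorithm. The argument rests on precision alone.

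**The missing between-arm test matters more.** Agreed. In a self-described pilot, preferring ANCOVA to a valid change-score test is an efficiency improvement rather than the correction of an error. Still, repairing only the test would leave this loss in place, and one model settles both.

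**The SAP is written in the past tense.** If outcome data have already been seen, the adjustment would be post hoc and should be reported as such.

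**Conclusion.** The point holds as a matter of precision. Baseline enters by pairing, differencing or ratio, never as a covariate in an ITU-versus-sham comparison, and neither document names a test that compares the two arms. Against a between-arm change-score test, ANCOVA would remove 35%, 25% or 15% of the variance at ρ = 0.3, 0.5 or 0.7. That rests on 25 analysed per arm, equal SDs at both times, a two-sided 0.05 level, and correlations assumed rather than taken from the documents. It does not follow that the trial is invalid or that the plan leaves baseline out. The change is worth making because its gain is real over the whole range and its cost is slight.

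**What to change.** In the Protocol's Statistical analysis paragraph and in the SAP's Statistical Calculations:

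1. Replace the paired and Student t-tests with a regression of the follow-up value on arm and the subject's own week-0, pre-treatment value (ANCOVA, or a repeated-measures model with baseline as covariate). Apply it to PFCAT, FFI-P, FAAM and fascia thickness, and to the SAP's pain score and lesion volume.
2. Name one time point for the main comparison, after reconciling the follow-up weeks: 2, 4, 6, 12 and 24 in the Protocol against 4, 8, 12 and 26 in the SAP.
3. Report the adjusted ITU-minus-sham difference with its 95% confidence interval. Keep percentage reductions and within-arm changes as description.

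**Cost.** One degree of freedom per model and a short edit to both documents, which includes adding PFCAT, FAAM and thickness to the SAP. No new data, subject or visit.
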